## Study Design & Methodology

This is a randomized, parallel-group, double-blind, exploratory two-arm trial to assess the effects of CBD on driving ability along with changes in psychological status (e.g., sedation) and cognitive function. Thus, the data will be collected prospectively. The methodology of the study is below.

**Study Design and Protocol Overview.** We propose a randomized, parallel-group, double-blind, exploratory two-arm trial to assess the effects of CBD on driving ability along with changes in psychological status (i.e., mood, drowsiness, sedation) and cognitive function. Forty healthy West Virginia University (WVU) students will be allocated and randomized to receive: (1) 300 mg of pure CBD oil or (N=20) (2) placebo matched in appearance and taste (N=20). After consuming the study drug, each individual will participate in a 25–35-minute driving simulation, which includes a practice drive and brake reaction test, and their driving performance measured. To assess changes in psychological status (i.e., mood, drowsiness, sedation) and drug impairment-related cognitive function, the VAMS, SSS, DSST, TMT, PVT, SRT will also be administered to participants at baseline (prior to study drug consumption) and following completion of the driving simulation test. The primary outcome of this study will be driving performance, quantified using measures strongly associated with collision risk including number of lane departures, standard deviation of lateral position (i.e. weaving), reaction time, and collision occurrence. Secondary outcomes will be pre-post changes in well-validated measures of mood, drowsiness, mental sedation (VAMS, SSS) and cognitive function (DSST, TMT, PVT, SRT). We will also collect baseline demographic, health (including body mass index), and driving history data, including driving habits, along with data at the end of the survey to assess participant satisfaction and tests of

blinding. The entire protocol will be completed in one day and should take 4-4.5 hours to complete for each participant. We chose a parallel RCT design as opposed to a cross-over RCT to minimize participant burden, while still being able to study both within individual (i.e., test battery results) and between group effects (i.e., simulator and test battery performance).

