These tests have all been deemed valid and reliable instruments and have been described in detail elsewhere. The tests will be administered by trained study personnel via a computer tablet and/or paper and pencil; personnel will then transfer the collected data to a secure, electronic database. Participants will also be given a standardized breakfast after baseline assessment.

**Allocation, Randomization and Blinding.** Participants will be randomized immediately after baseline assessments are completed to the CBD (N=20) or placebo group (N=20) using a sex-stratified 1:1 random block design to ensure equal distribution among treatment groups and sex. The participant and the PI will be unaware of group assignment (i.e. double-blind). [name], who will not have contact with participants, will generate a randomized assignment master list and provide sequentially numbered envelopes containing group assignment to the team member that helps consent participants. This team member will assign the unique number from the next envelope in sequence as the participant's study identification number and will record the participant's information in a secure, electronic master database.

**Intervention.** Protocol A consists of a 300 mg dosage of CBD oil which will be consumed orally. This dosage was chosen as it has been used in other studies consisting of both healthy and clinical populations and is well-tolerated with no major adverse events. CBD will be obtained from Zatural, a CBD manufacturer from Eden, Idaho. The CBD oil will be tested by Botanacor Laboratories (Denver, CO) for microbials, potency, heavy metals, trace THC, pesticides, and residual solvents to ensure purity, label accuracy, and safety; copies of laboratory reports will be maintained on premise. Protocol B is a placebo matched on appearance to the treatment (i.e., avocado oil potentially colored with food coloring). Both the CBD oil and placebo will be matched on taste (i.e., peppermint-flavored oil) prior to dispensing to each participant. After consumption of the respective protocol drug, the participant will be given a standardized meal and will then wait for 120 minutes to allow for digestion and for CBD to begin taking effect; this time frame was chosen based on the pharmacodynamics of CBD along with the consideration of participant burden (max absorption 2-5 hours). Next,

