tests of blinding by comparing accuracy of group assignment (perceived group assignment will be asked on end of study survey). If differences are noted, models can be adjusted. For between group effects, the data will be compared using Student's T-tests and/or ANOVA for continuous variables if the data are normally distributed; if non-normally distributed a Mann-Whitney test may be utilized. For within group effects, the data will be compared using paired Student's T-tests (for normally distributed continuous paired observations ) or Wilcoxon signed-rank test (for those continuous paired observations not normally distributed). We will perform a correlation using Pearson's R test between the variables collected for Aims 1 and 2, both between and within groups, to assess whether driving performance is

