## Statistical Analysis Plan

All collected data will be entered by study staff into the secure, de-identified database and maintained in accordance with WVU IRB. All analyses will be performed in SAS (Cary, NC). The primary outcome of this study will be driving performance, including number of lane departures, standard deviation of lateral position (i.e., weaving), mean brake reaction time, and number of collisions (Aim 1). Secondary outcomes will be pre-post changes in well-validated measures of mental sedation (SSS, VAMS) and cognitive function (DSST, TMT, PVT, SRT) (Aim 2). The variables that will be collected and their source are summarized in Table 2. Missing data will be multiply imputed to allow inclusion of all participants regardless of compliance. We will perform both an intent-to-treat analysis based on initial assignment and a protocol

analysis, excluding those who fail to complete the study. Both between and within-group analyses will be conducted. Demographic characteristics will be compared between groups via descriptive statistics to ensure proper randomization; we will also investigate tests of blinding by comparing accuracy of group assignment (perceived group assignment will be asked on end of study survey). For between group effects, the data will be compared using Student's T-tests and/or ANOVA for continuous variables if the data are normally distributed; if non-normally distributed a Mann-Whitney test may be utilized. For within group effects, the data will be compared using paired Student's T-tests (for continuous paired observations which are normally distributed) or Wilcoxon signed-rank test (for continuous paired observations which are not normally distributed). We will perform a correlation using Pearson's R test between the variables collected for Aims 1 and 2, both between and within groups, to assess whether driving performance is correlated with psychological or cognitive testing measures. Data will also be analyzed via sex.

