**Sample Size** – We conducted an analysis to ensure adequate sample size and power. The analysis was based on mean reaction time, which is one of the primary outcomes between groups. A total sample size of 26 students with a large effect size of 0.7 and  $\alpha=0.05$  using a two-sided, two-sample equal variance t-test achieves 80% power to reject the null hypothesis of equal means. Thus, our total sample size (N=40) should be more than adequate for this study.

**Data Safety Monitoring** – A Data Safety Monitoring Board will not be appointed for this study unless required.

 Table 2. Overview of proposed variables to be collected and for CBD studya

Aim	Variables	Source
	Socio-demographics, driving history, health	Baseline questionnaire
Aim 1. Determine the effects of CBD on the driving performance of healthy adults aged 18-30 years.	Driving performance 
 
Number of lane departures
 
Number of collisions
 
Mean brake reaction time to stimuli
 
Mean standard deviation of lateral position in lane under consistent speed
 
	Driving simulation
Aim 2. Determine the effects of CBD on participants psychological status and cognitive function.	Sedation 
 
Self-reported sleepiness
 
Mental sedation: Sum of scores from questions 1,4,11,13 on VAMS—higher scores indicate more mental sedation
 
Physical sedation: Sum of scores from questions 3,5,6,16 on VAMS—higher scores indicate more physical sedation
 
 Cognitive function 
 
Number of symbols completed within 60 seconds
 
Number of correct symbols completed within 60 seconds
 
Time to accurately complete Part A and Part B
 
Mean reaction time to stimuli
 
Mean reaction time to stimuli
 
	SSS VAMS VAMS DSST TMT PVT SRT
Aim 3. Determine the relation of driving performance to changes in psychological and cognitive status.	Correlation between variables in Aims 1 and 2	Driving simulation outcomes, SSS, VAMS, DSST, TMT, PVT, SRT

a: All measures will be assessed between treatment and placebo groups. DSST, SSS, TMT, PVT, SRT and VAMS scores will also be compared within subjects to gauge changes overtime.

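### The SAP does not say whether change or the post-drive score is compared between arms for the nine battery scores, and it pre-specifies no baseline adjustment that would usually sharpen that comparison

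*Combined protocol and SAP*

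**What the plan says.** The battery (VAMS, SSS, TMT, DSST, PVT, SRT) is given before dosing and again after the drive (Study Design & Methodology). The Statistical Analysis Plan section states: "Secondary outcomes will be pre-post changes in well-validated measures of mental sedation (SSS, VAMS) and cognitive function". For comparing arms it says: "For between group effects, the data will be compared using Student's T-tests and/or ANOVA for continuous variables if the data are normally distributed". A Mann-Whitney test may be used if the data are not normal. No covariate is named, and the variable being tested is called only the data.

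The footnote to Table 2 says "All measures will be assessed between treatment and placebo groups", and then "DSST, SSS, TMT, PVT, SRT and VAMS scores will also be compared within subjects to gauge changes overtime".

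Adjustment is mentioned once, in the Data Collection, Management and Analysis paragraph of Study Design & Methodology. After checks of demographics, driving habits and blinding it says "If differences are noted, models can be adjusted". The Statistical Analysis Plan section does not repeat this.

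Randomisation uses a "sex-stratified 1:1 random block design". The SAP adds "Data will also be analyzed via sex", but does not put sex into the between-arm comparison.

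**The concern.** Two analysts could follow this text faithfully and test different variables for every battery score, one the post-drive value and the other the change. At 20 per arm the two can differ a good deal in precision, and which is better depends on a correlation that nobody has stated.

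A baseline value is planned for every participant. Adjusting for it in a model fixed in advance usually gives a narrower interval than either simple test. The sentence that permits adjustment does not do this job: it is optional, it depends on differences seen in the data, and it names no covariate. At stake are the precision of the secondary estimates and the freedom to choose among analyses after seeing the data.

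**Working it through.** **Inputs from the documents.** There are 20 per arm with 1:1 allocation (Allocation, Randomization and Blinding), and two-sided alpha is 0.05 (Sample Size). Table 2 lists nine battery scores: SSS 1 + VAMS 2 + DSST 2 + TMT 2 + PVT 1 + SRT 1 = 9.

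**Inputs assumed.** The documents give no pre-post correlation r, no SD and no effect size for these scores. The 0.7 SD effect is borrowed from the Sample Size paragraph, where it refers to mean reaction time as a primary outcome. It is used here only for illustration. The plan has no power figure of its own for the battery scores, so there is nothing to reproduce first.

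**Formulas.** The variance of the estimated arm difference is (2 × SD² / 20) × F, where SD is the post-drive SD and k is the ratio of the pre SD to the post SD:

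- t-test on post score: F = 1
- t-test on change: F = 1 + k² − 2rk, which is 2(1 − r) when k = 1
- ANCOVA on baseline: F = (1 − r²) × (1 + 1/36), the last factor being the small-sample cost of one covariate at N = 40

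Power comes from the noncentral t distribution with noncentrality 0.7 × √(10/F).

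**Example at r = 0.5, k = 1.** For both post and change F = 1, noncentrality is 0.7 × √10 = 2.21 and power is 57.8%. For ANCOVA F = 0.75 × 1.028 = 0.771, noncentrality is 2.21/0.878 = 2.52 and power is about 69%.

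**Results, k = 1, normal data.** ANCOVA here includes baseline and sex (36 residual degrees of freedom) and is averaged over chance baseline imbalance. Half-widths are expected 95% CI half-widths in SD units.

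| r | Power: post | Power: change | Power: ANCOVA | Half-width: post / change / ANCOVA |
|---|---|---|---|---|
| 0.3 | 57.8% | 44.6% | 60.6% | 0.64 / 0.75 / 0.62 |
| 0.5 | 57.8% | 57.8% | 68.9% | 0.64 / 0.64 / 0.56 |
| 0.7 | 57.8% | 79.5% | 84.5% | 0.64 / 0.49 / 0.46 |
| 0.8 | 57.8% | 92.7% | 94.3% | 0.64 / 0.40 / 0.39 |

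Simulation agrees with these figures.

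**Where ANCOVA does not win.**

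- Low correlation: at r = 0 it has 56.6% against 57.8% for post scores. It breaks even near r = 0.2.
- Pre SD 0.8 of the post SD: against change it has 84.5% against 84.9% at r = 0.7, and 94.3% against 94.9% at r = 0.8. With a 0.5 SD effect the largest such loss is 1.3 points (71.6% against 72.9% at r = 0.8).
- Pre SD 1.25 times the post SD: the balance reverses, and ANCOVA leads change by 12 to 25 points over r = 0.3 to 0.8.

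**Skewed scores.** Simulated lognormal data with log-SD 1.0 and an effect of 0.7 on the log scale, at r = 0.3, 0.5 and 0.8:

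| Analysis | Power |
|---|---|
| ANCOVA on the raw scale | 42 / 48 / 72% |
| Mann-Whitney on change | 44 / 56 / 89% |
| Mann-Whitney on post score | 56 / 55 / 57% |
| ANCOVA on the log scale | as in the normal-data table: about 61 / 69 / 94% |

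On the raw scale ANCOVA loses up to 89 − 72 = 17 points to a test that the plan already allows. On the log scale it does not.

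**The case against.** The strongest reply is that the natural reading of the SAP already uses baseline. The secondary outcomes are defined as changes, and Aim 3 in Table 2 also relates driving to changes in psychological and cognitive status. A t-test on change takes baseline into account, and the further gain from ANCOVA is then about 5 points at r = 0.7 and under 2 at r = 0.8. This stands. It limits the gain at high correlation, though not at r = 0.3 to 0.5, and it does not remove the ambiguity about what is tested.

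A reader might infer more than the documents support:

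- That the planned comparisons are biased or invalid. They are not; either variable gives a valid test of CBD against placebo in a randomised trial.
- That the raw scores listed in Table 2 show that post-drive scores will be tested. The table presents itself as an overview of variables to be collected, so it does not settle the matter.
- That conclusions about CBD will rest on within-arm p-values. No passage says so, and the footnote presents the within-subject comparison as additional to the between-arm one. What is missing is only a statement that the paired tests are descriptive.

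It is also fair to object that replacing Mann-Whitney with a raw-scale linear model could do harm. The skewed-data results confirm it, which is why the scale must be part of the specification.

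**Conclusion.** The point holds as a worthwhile improvement, not as an error. The SAP leaves the between-arm variable for nine secondary scores unstated and pre-specifies no baseline adjustment, although baseline is measured.

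Under the equal-SD, normal-data assumptions with a 0.7 SD effect, the gain over r = 0.3 to 0.8 runs from about 3 to 37 power points against post scores and from about 16 down to 2 against change scores. The result depends on the assumed correlation, SD ratio, effect size and distribution, none of which the documents give for these scores. ANCOVA is usually, not always, the more precise choice, and for strongly skewed scores only on a suitable scale.

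The point does not extend to the primary driving outcomes. The protocol describes a pre-dose practice drive to detect simulator sickness, but no baseline driving measurement.

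**What to change.** For each of the nine battery scores, pre-specify one between-arm ANCOVA: post-drive score on arm, baseline score and sex. Sex enters because it stratifies randomisation; no power gain is claimed for it. Report the adjusted difference with its 95% CI, pooled over the planned imputations.

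Fix the scale before unblinding:

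- **TMT A, TMT B, PVT, SRT:** log-transform at both time points and report ratios.
- **SSS:** use a rank-based or ordinal baseline-adjusted model of the post-drive score, and state what it reports, because it gives no score-scale difference.
- **VAMS mental and physical sums, DSST completed and correct:** use the raw scale.

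In the linear models the arm effect is the same whether the post-drive score or the change is the dependent variable (log change for the timed scores), so the definition as change can stay. For the SSS the two are not equivalent, so the post-drive score must be named.

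State that, for these scores, this replaces both the normality-triggered switch of test and the optional adjustment after observed differences. State also that conclusions about CBD rest on the between-arm estimate and that the within-arm paired tests are descriptive.

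Cost: SAP wording only, with no new data. The models are standard in SAS; a rank-based model must be ranked within each imputed data set. The price is two degrees of freedom, about 1 point of power against post scores if r is near 0, and roughly half a point to 1 point against change at high r if the pre SD is 0.8 of the post SD.

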**Consent, Screening, and Baseline Assessments.** Students who are interested in participating in the study will be contacted via study personnel. Participants will be given a brief overview of the study and its purpose and will be initially screened for eligibility using a standardized screening checklist. If the individual meets the inclusion and exclusion criteria, they will be invited to participate in the study. Participants will be given a list of instructions prior to their assessment. While participants should not be taking any routine prescription medications as part of the inclusion criteria, they will be told to abstain from taking any other types of medications including nutraceuticals, over-the-counter medications, vitamins, supplements 24 hours prior to coming to their appointment. Caffeine and alcohol should also not be consumed within 10 hours of their appointment. They will be instructed to get at least 6 hours of sleep the night prior and to only consume water prior to their scheduled visit.

At the research office, study personnel will explain the requirements, re-screen the participant, and review the consent form with each individual in a private room and obtain signed consent. After consenting, the participant will be asked to provide a urine sample which will be analyzed immediately onsite for potentially impairing or illicit drugs via a rapid urine test. If the individual tests positive for any potentially impairing substance, they will not be able to participate in the study. Anyone who tests positive for a drug will be referred to the Carruth Center on campus. If a participant's sample tests negative, they will then be allowed to practice on the driving simulator for approximately 10 minutes prior to engaging in any other study activities. This is necessary as some individuals who are prone to motion sickness may experience brief, mild nausea (e.g., simulator sickness). If there is evidence of simulator sickness, the individual will not be able to participate in the study, as they will likely not be able to complete the

protocol. Any reasons as to why an individual is not eligible to participate will be documented in a screening log. If no simulation sickness is observed, the student will then take the standardized and pilot-tested baseline survey regarding their demographics, health (including body mass index), and driving history along with the VAMS, SSS, TMT, DSST, PVT, and SRT tests.

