**Table 2. Overview of proposed variables to be collected and for CBD studya**

Aim	Variables	Source
	Socio-demographics, driving history, health	Baseline questionnaire
Aim 1. Determine the effects of CBD on the driving performance of healthy adults aged 18-30 years.	
Driving performance
 
 
Number of lane departures
 
Number of collisions
 
Mean brake reaction time to stimuli
 
Mean standard deviation of lateral position in lane under consistent speed
 
	Driving simulation
Aim 2. Determine the effects of CBD on participants psychological status and cognitive function.	
Sedation
 
 
Self-reported sleepiness
 
Mental sedation: Sum of scores from questions 1,4,11,13 on VAMS—higher scores indicate more mental sedation
 
Physical sedation: Sum of scores from questions 3,5,6,16 on VAMS—higher scores indicate more physical sedation
 
 
Cognitive function
 
 
Number of symbols completed within 60 seconds
 
Number of correct symbols completed within 60 seconds
 
Time to accurately complete Part A and Part B
 
Mean reaction time to stimuli
 
Mean reaction time to stimuli
 
	
SSS VAMS
 
VAMS
 
DSST
 
TMT
 
PVT SRT

Aim 3. Determine the relation of driving performance to changes in psychological and cognitive status.	Correlation between variables in Aims 1 and 2	Driving simulation outcomes, SSS, VAMS, DSST, TMT, PVT, SRT

a: All measures will be assessed between treatment and placebo groups. DSST, SSS, TMT, PVT, SRT and VAMS scores will also be compared within subjects to gauge changes overtime.

correlated with psychological or cognitive testing measures. Data will also be analyzed via sex as well.

As one can see, there is minimal risk to participants. There is no direct benefit to participants. However, there are potential benefits to society that offset the potential risks of this study, which are minimal. The findings of this study will be extremely informative to the public, medical providers, policy makers, and public health practitioners.

Cannabidiol is commonly used drug, yet its effects in healthy populations are virtually unknown. Thus, the risk vs. benefit is reasonable.

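### Brake reaction time is compared between arms without adjustment, although every participant has a pre-randomization reaction-time score that could be prespecified as a covariate at almost no cost

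*Combined protocol and SAP*

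**What the plan says.** The Statistical Analysis Plan lists four driving measures as the primary outcome: lane departures, standard deviation of lateral position, mean brake reaction time and collisions. For the comparison of arms it says "For between group effects, the data will be compared using Student's T-tests and/or ANOVA for continuous variables if the data are normally distributed", with Mann-Whitney as the option for non-normal data. It names no covariate. Sex, the stratification factor, appears only as a variable by which the data will also be analysed.

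Under Consent, Screening, and Baseline Assessments (Study Design & Methodology), each participant completes a baseline survey covering "driving history along with the VAMS, SSS, TMT, DSST, PVT, and SRT tests". Under Allocation, Randomization and Blinding, randomization comes directly after these assessments. Table 2 scores PVT and SRT as mean reaction time to stimuli, and the driving outcome as mean brake reaction time to stimuli.

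Two other places bear on the point:

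- The Data Collection, Management and Analysis paragraph of the protocol allows models to be adjusted if differences are noted. The sentence follows comparisons of demographics, driving habits and blinding guesses. It is optional, names no test score, and is not repeated in the Statistical Analysis Plan section.
- Table 2 gives "Aim 3. Determine the relation of driving performance to changes in psychological and cognitive status". The analysis text says this is done by correlation, to find out whether the two are related.

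On size, the Sample Size paragraph says "The analysis was based on mean reaction time, which is one of the primary outcomes between groups" and concludes "Thus, our total sample size (N=40) should be more than adequate for this study".

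**The concern.** People differ in reaction speed before they take any study drug. In a parallel design with 20 per arm and a single post-dose drive, that stable difference between people stays in the error term of the brake reaction time comparison. A baseline score that predicts brake reaction time would remove part of it, and would also correct for chance imbalance in reaction speed between arms.

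The scores are already collected from everyone, before randomization, so they are legitimate covariates. At stake is the precision of the comparison on which the sample size appears to rest. The adjustment sentence in the protocol does not settle this: a covariate chosen after differences have been seen leaves discretion to the analyst, whereas a named one does not.

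**Working it through.** **Inputs.** From the Sample Size paragraph: standardized effect d = 0.7, two-sided alpha 0.05, two-sample equal-variance t-test, 80% power. Planned N = 40, 20 per arm. The powered endpoint, mean reaction time, is read as brake reaction time. The correlation r between pre-dose SRT and post-dose brake reaction time is not in the documents and is varied.

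**The plan's own figure.** The claim is "A total sample size of 26 students with a large effect size of 0.7" and that the comparison "using a two-sided, two-sample equal variance t-test achieves 80% power to reject the null hypothesis of equal means". The noncentrality is d × √(n/2), with n per arm.

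- At 13 per arm: 0.7 × √6.5 = 1.785 on 24 df, power 40.3%. The stated 80% does not reproduce.
- 80% power needs 34 per arm, 68 in total.
- At the planned 20 per arm: 0.7 × √10 = 2.214 on 38 df, power 57.8%. The effect detectable with 80% power is d of about 0.91.

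So the brake reaction time comparison has no power to spare, which is why an efficiency gain is worth considering.

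**With one baseline covariate.** Three things change:

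- Residual variance is multiplied by (1 − r²), so the effect in residual SD units is 0.7/√(1 − r²).
- One degree of freedom is lost: 37 instead of 38.
- Chance imbalance in the covariate inflates the variance by about 1 + 1/(N − 4) = 1 + 1/36, a factor of √1.0278 = 1.0138 on the standard error.

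Noncentrality = 2.214 / (√(1 − r²) × 1.0138). For r = 0.5: 2.214 / (0.866 × 1.0138) = 2.521 on 37 df, power 69.0%.

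| r | √(1 − r²) | Power, formula | Power, simulation | Change from 57.8% (simulation) |
|---|---|---|---|---|
| 0 | 1.000 | 56.6% | 56.5% | −1.3 |
| 0.2 | 0.980 | 58.3% | 58.4% | +0.6 |
| 0.3 | 0.954 | 60.6% | 60.6% | +2.8 |
| 0.4 | 0.917 | 64.1% | 64.3% | +6.5 |
| 0.5 | 0.866 | 69.0% | 68.9% | +11.1 |
| 0.6 | 0.800 | 75.7% | 75.8% | +18.0 |

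The simulation generates the two-arm data and fits the adjusted model, so it carries the imbalance cost directly. Power equals the unadjusted 57.8% at r of about 0.17 and reaches 80% at r of about 0.66.

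**Adding sex.** If sex explains nothing and were left to chance, the two-covariate figures would be 55.4% (r=0), 59.3% (0.3), 67.7% (0.5) and 74.5% (0.6). Stratified randomization should keep sex close to balanced, so the real cost should be nearer to one further degree of freedom (36 instead of 37), about 0.1 point. If sex does explain some brake reaction time variance, the cost falls or reverses.

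**The case against.** The strongest case against is that nothing here is an error. An unadjusted comparison of randomized arms is valid and unbiased, and the trial calls itself exploratory. The gain depends wholly on an r that the documents do not give, is modest unless r is about 0.5 or more, and turns into a small loss below about 0.17. SRT is a tablet task and brake reaction time a simulator measure, so a strong correlation cannot be taken for granted. All of this stands, and it limits the point to a cheap improvement.

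A reader might infer more than the documents support:

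- *That the plan contradicts itself because Aim 3 presumes these tests track driving.* It does not. Aim 3 asks whether they are correlated, and Table 2 frames it around changes in status, not the pre-dose score as a predictor.
- *That the precision is free and certainly being thrown away.* Neither is shown. The covariate uses a degree of freedom and carries a chance-imbalance cost.
- *That the plan leaves no room for adjustment.* The protocol does allow it. The gap is that the allowance is optional, follows observed differences and names no score.
- *That the same model should serve every driving outcome.* Lane departures and collisions are counts. For lateral position, no document text or calculation supports a PVT or SRT covariate.

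**Conclusion.** The point holds as an inexpensive improvement to one comparison, brake reaction time. The planned test is valid but may be less precise than the collected data allow. Going by the table, one prespecified baseline reaction-time covariate would change power by anything from a loss of about 1 point (r=0) to a gain of about 3 points (r=0.3), 11 points (r=0.5) or 18 points (r=0.6).

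This rests on d = 0.7 being a standardized mean difference, on the powered mean reaction time being brake reaction time, on roughly normal residuals (after a log transform if needed), and on an assumed range for r.

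Adjustment does not rescue the sample-size statement. Only if r were about 0.66 or higher would 40 participants give 80% power at the plan's effect size, and nothing in the documents indicates such a value.

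**What to change.** State in the Statistical Analysis Plan that:

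- brake reaction time is compared between arms by a linear model with arm, pre-dose SRT mean reaction time and sex (the stratification factor), on the log scale if reaction times are skewed;
- the model is fixed before unblinding and applied whatever baseline imbalance is observed;
- the unadjusted comparison is reported as a sensitivity analysis.

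Say how this relates to the protocol sentence on adjusting when differences are noted, so that it is clear which analysis is primary for this outcome. Any statement of expected gain should give the r assumed. Keep this linear model away from lane departures and collisions.

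The cost is a few lines of SAP text and one model statement in SAS. No new data, visits or participant burden are needed. The downside is the two degrees of freedom used and about 1 point of power if SRT turns out to be unrelated to brake reaction time.

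### Aim 3 does not define its between-group correlation or name a lead analysis; if the arms are pooled, no arm term is specified, and an arm-adjusted partial correlation would be a free improvement.

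*Combined protocol and SAP*

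**What the plan says.** The Statistical Analysis Plan section and the paragraph on data collection, management and analysis under Study Design & Methodology carry the same sentence for Aim 3: "We will perform a correlation using Pearson's R test between the variables collected for Aims 1 and 2, both between and within groups". The stated purpose is "to assess whether driving performance is correlated with psychological or cognitive testing measures".

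Table 2 words the aim as "Determine the relation of driving performance to changes in psychological and cognitive status" and gives the analysis as "Correlation between variables in Aims 1 and 2". It does not state the level of analysis, how arm is handled, or which result leads.

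The only adjustment language is in the Study Design & Methodology paragraph: "If differences are noted, models can be adjusted". It follows the comparison of baseline characteristics and the check of blinding, and the SAP section does not repeat it. Participants are allocated "to the CBD (N=20) or placebo group (N=20) using a sex-stratified 1:1 random block design".

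**The concern.** For group comparisons, a between-group analysis has a plain meaning. For a correlation it does not. It could mean one correlation over all 40 participants, or a comparison of the two arms' correlations. Because the stated purpose is to learn whether driving and test scores are related, and not whether that relation differs by arm, pooling is a natural reading.

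Pooling without an arm term mixes two things: the link between driving and test score among people on the same treatment, and the difference between arms on each measure. If CBD both sedates and impairs driving, as the trial sets out to test, the second part alone yields a positive correlation. Aim 3 would then partly restate Aims 1 and 2. The distortion can also hide a link, if CBD moves the two measures in directions that oppose their within-arm relation.

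**Working it through.** **The plan's own figure.** No power or sample-size figure is given for Aim 3. The one calculation in the plan, for mean reaction time, reads "A total sample size of 26 students with a large effect size of 0.7 and" a two-sided 5% test, with 80% power. That figure does not reproduce. The normal approximation gives 2 × (1.960 + 0.842)² / 0.7² = 32.04, so 33 per arm (66 in total); the t-test gives 34 per arm (68 in total). This is a separate matter and does not bear on the present point. Only the 0.7 is borrowed here, as a reference effect size.

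**Inputs.**
- From the documents: 20 per arm, 1:1 allocation. The 5% two-sided level is the one used in the sample-size calculation.
- Assumed: CBD effects d1 (driving measure) and d2 (test score), in within-arm SD units, from 0 to 1.5; normal data; a within-arm correlation of 0 unless stated.

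**Correlation created by arm alone.** With half the participants in each arm, the arm difference adds d1·d2/4 to the covariance and d²/4 to each variance. With zero within-arm correlation:

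r = (d1·d2/4) / √[(1 + d1²/4)(1 + d2²/4)]

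- 0.7 and 0.7: 0.1225 / 1.1225 = 0.109
- 1.0 and 1.0: 0.25 / 1.25 = 0.20
- 0 and 0.7: 0

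**Simulated rate of significance** (100,000 trials per row, 20 per arm, two-sided 5%, within-arm correlation 0):

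| Effect on driving / test (SD) | Mean pooled r | Pooled, significant | Arm-adjusted, significant | One arm (n = 20), significant |
|---|---|---|---|---|
| 0 / 0.7 | 0.00 | 5% | 5% | 5% |
| 0.5 / 0.5 | 0.06 | 6.5% | 5% | 5% |
| 0.7 / 0.7 | 0.11 | 10% | 5% | 5% |
| 0.7 / 1.0 | 0.15 | 15% | 5% | 5% |
| 1.0 / 1.0 | 0.20 | 24% | 5% | 5% |
| 1.5 / 1.5 | 0.37 | 68% | 5% | 5% |

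**Masking.** With a true within-arm correlation of 0.3 and opposite effects of 0.7 SD, the pooled value is (0.3 − 0.1225) / 1.1225 = 0.158 by formula and 0.15 in simulation. The arm-adjusted mean is 0.30.

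**Power of the two analyses that are free of the arm effect.** The critical |r| is 0.444 with n = 20, and 0.316 for the partial correlation in all 40 (37 degrees of freedom). For an assumed true within-arm correlation of 0.4, simulated power is 43% in one arm and 73% for the partial correlation. A check with Fisher's z, where atanh(0.4) = 0.4236:
- One arm: 0.4236 × √17 − 1.960 = −0.213, power 42%.
- Partial: 0.4236 × √36 − 1.960 = 0.582, power 72%.

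**The case against.** A reader might infer that the plan never removes the arm effect, so that a drug effect is bound to be reported as a link. The documents do not support this. The same sentence plans within-group correlations, which carry no arm effect, and nothing ranks them below the other version. Pooling is also only one reading: elsewhere in the SAP section, between-group effects means comparing the arms.

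A reader might also infer that the within-arm analyses lose most of their power. They do not: 43% against 73% keeps 43/73, or about 59%. The 0.4 is an assumption, and the plan sets no power target for this aim.

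Nor does the plan leave the choice of variables wholly open. The SAP section defines the Aim 2 outcomes as pre-post changes, and Table 2 words Aim 3 in terms of changes. Change scores are the natural reading and only need stating.

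The size of the problem is conditional. Inflation needs an effect on both measures, and the 0.7 in the plan applies to reaction time only. The Background section says earlier healthy-volunteer studies did not differ significantly from placebo, so 1.0 SD on both measures has no support in the documents.

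The best remaining argument is that adjusting for arm changes the question. If CBD impairs driving through sedation, part of the relation runs through arm, and a partial correlation removes that part. This is fair, and it is a reason to keep showing the unadjusted value. It is not a reason to lead with it: a pooled correlation cannot tell that pathway from two unrelated drug effects.

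**Conclusion.** The concern holds in a limited form. The plan leaves the between-group correlation undefined and does not say which result answers Aim 3. If the arms are pooled, no arm adjustment is named, and the optional adjustment for baseline or blinding differences does not supply one.

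The consequence depends on the CBD effects, which are unknown. There is no inflation if only one measure is affected. At 0.7 SD on both, the false-positive rate is about 10%; at 1.0 SD on both, it is 24%. These rates assume normal data, 20 per arm and zero within-arm correlation.

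The within-arm correlations are valid but use half the sample each. The arm-adjusted correlation improves on both planned versions: it holds the 5% level and uses everyone. The trial is described as exploratory, and the Aim 3 correlations are neither a primary nor a secondary outcome, so this is a minor improvement.

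**What to change.** In both places where the Aim 3 sentence appears:

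1. Name the lead analysis: a partial correlation adjusted for arm, in all 40 participants, between each driving measure and the pre-to-post change in each test score.
2. Use the rank version for lane departures, collisions and the SSS. The first two are counts and the SSS is a single item. The SAP offers rank-based alternatives for group comparisons but none for correlations.
3. Report the per-arm and the unadjusted pooled correlations as descriptive only, and label each as such.

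This does not deal with multiplicity. Table 2 yields 4 driving measures × 9 test measures = 36 pairs, so about 36 × 0.05 = 1.8 would be significant by chance if no links existed. The write-up should say so.

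The cost is a short addition to the SAP text and one extra term in the code. No new data are needed and the sample size is unchanged.
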